Proper workup of anisocoria that is greater in bright light is extremely important given the potentially dangerous causes of an inappropriately dilated pupil. Particularly, the reaction of the anatomically intact, inappropriately dilated pupil to 1% pilocarpine can be essential in distinguishing pharmacologic dilation from dilation caused by a third nerve palsy. Although third nerve palsies are often associated with ophthalmoplegia in addition to mydriasis, isolated mydriasis of the affected pupil can be seen in the early stages of compressive damage to the nerve.¹ Whereas pharmacologic dilation is a benign condition that involves no further workup, compressive third nerve palsy is a common presenting sign of conditions such as subarachnoid hemorrhage, intracranial mass, intracranial aneurysm, or cavernous sinus aneurysm.¹⁻³

If the current algorithm is followed, any anatomically intact, yet inappropriately dilated eye that contracts to 1% pilocarpine, but not to 0.1%, will be considered suspicious for a third nerve palsy. Our proposal to clarify the “wearing-off” period of pharmacologic dilation will provide those utilizing this algorithm with an alternative etiology for a pupil that constricts to 1% pilocarpine. This addition will help to avoid unnecessary and expensive workup for a suspected third cranial nerve palsy.

Currently, there is not any literature that describes the “wearing-off” period of pharmacological dilation as a cause of anisocoria in respect to acute clinical workup. Although there are examples of recent studies describing the potential use of constricting agents to reverse pharmacologically induced mydriasis, these studies have been limited in scope to symptomatic relief from the dilated eye and thus have not influenced the BCSC algorithm for the treatment of anisocoria in the acute setting.⁴ We believe that this study has the potential to save money and time, as well as reduce the stress that may be associated with consideration of a more serious diagnosis. These benefits will be applicable to the provider, as well as the patient, thus advancing patient-centered high-quality care.

C. PRELIMINARY STUDIES

There are no preliminary studies that are pertinent to this protocol.

[name], DO is a board-certified ophthalmic plastic & reconstructive surgeon. He will be overseeing the project’s academic and clinical aspects. He has completed CITI training through Prisma Health to conduct human subjects research.

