In the event that no response to 1% pilocarpine is observed at the initial post-dilation visit, or if pupillary diameter has returned to baseline prior to the administration of 1% pilocarpine at any point, we will ask this participant to return to the clinic on another day to have the process repeated in their right eye, with the modification of either shortening or lengthening the interval of reassessment based on their left eye's response to the drops. This is to avoid any confounding from the administration of subsequent pilocarpine eye drops in the same eye. If the left pupil returned to baseline pupillary diameter prior to the 3-4 hour reassessment, we will have them return 2-3 hours following dilation of their right eye to have their pupillary diameter checked and the administration of Pilocarpine 1% repeated. If the left pupil remained dilated with no response to 1% pilocarpine at 3-4 hours, we will have them return 4-5 hours following dilation of their right eye to have their pupillary diameter checked and the administration of Pilocarpine 1% repeated. Repeating the protocol with varied assessment times in the contralateral eye will be in an effort to compensate for expected variation in each participant's response to tropicamide and 1% pilocarpine. Despite this, it is possible that we will not be able to capture this critical window in each participant, if one exists. However, we do not believe it will be necessary to demonstrate the phenomenon in all participants, and a minimum of 2 positive results should be sufficient to demonstrate our proposed concept for this preliminary study.

E. PROTECTION OF HUMAN SUBJECTS

1. TARGET POPULATION:

We plan to conduct the study with 15 medical student volunteers at the University of South Carolina Greenville. Exclusion criteria include a history of angle closure glaucoma, any other type of glaucoma, or any elevated eye pressure readings as well as any history of intraocular surgery or procedure. Exclusion will also occur if the participant is found to be hyperopic to >+1 diopter, has an intraocular pressure of > 22 mm Hg in either eye, or displays an iridocorneal angle where trabecular meshwork cannot be seen for greater than half of the angle in either eye, as these features are known to increase the risk of angle closure glaucoma when using dilating eye drops.

Finally, those with a known allergy to natural rubber latex will be excluded from the study.

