We chose a sample size of 15, as this is a proof of concept, and thus we would like to demonstrate a minimum of 2 instances of pharmacologically dilated eyes that constrict $> 1\text{mm}$ to 1% pilocarpine. We feel that at least 15 participants will be necessary to guarantee that we witness at least 2 instances of the proposed phenomenon, assuming that we test both of their eyes independently with varying timeframes of reassessment. If we limited the study to < 15 , we may not be able to witness the desired effect without subjecting participants to multiple rounds of testing.

If we are able to describe a period in which the pharmacologically dilated pupil responds to 1% pilocarpine with $>1\text{mm}$ of constriction but maintains the appearance of anisocoria that is worse in bright light in two or more participants, this study will serve as a pilot study to demonstrate the need for further research on the concept in order to make an addendum to the current treatment algorithm for anisocoria.

2. RECRUITMENT PLANS:

Recruitment of subjects will be done in person at the University of South Carolina School of Medicine Greenville, via the school newsletter that is sent to the student body on a weekly basis, and with email correspondence via the Ophthalmology interest group at the school. Approval has been obtained from school administration to conduct recruitment onsite and via electronic correspondence^{appx.6,7}.

3. EXISTING DATA/SAMPLES:

There are not any existing data or samples for this study.

4. CONSENT/ASSENT:

The participants will be asked to sign a consent form prior to participation^{appx.5}. The study doctor will consent the participants before any study procedures are completed. All communication will take place in a private setting. The participant will be given ample time to read the consent and have all questions answered prior to providing signature. The consent will be signed and dated by all parties and a copy will be provided to the participants at the time of consent. The consent will discuss risks of eye dilation including blurred vision for several hours following drop administration. Participants will also be informed of the risk of angle-closure glaucoma, and will be screened for any significant ophthalmological history, which will exclude them from the study. Participants will have ample opportunity to ask any questions concerning what to expect from and potential risks of dilating drops.

5. POTENTIAL RISKS:

Drug Tropicamide:

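### The protocol says 15 participants are needed to guarantee two positive results, but it gives no rate from which such an assurance could follow

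*Protocol*

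**What the plan says.** Section E.1 (Target Population) gives three reasons for 15 participants.

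- The study is a proof of concept that seeks at least 2 eyes meeting the constriction criterion.
- An assurance: "We feel that at least 15 participants will be necessary to guarantee that we witness at least 2 instances of the proposed phenomenon", on the condition "assuming that we test both of their eyes independently with varying timeframes of reassessment".
- With fewer than 15, "we may not be able to witness the desired effect without subjecting participants to multiple rounds of testing".

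The next paragraph of E.1 states the consequence by participant: if the phenomenon is described "in two or more participants, this study will serve as a pilot study to demonstrate the need for further research".

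Three other statements bear on the assurance.

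- Section C (Preliminary Studies): "There are no preliminary studies that are pertinent to this protocol".
- Section D (Research Design and Methods and Data Analysis), on when the right eye is used: "In the event that no response to 1% pilocarpine is observed at the initial post-dilation visit", or if the pupil is back at its baseline diameter before pilocarpine is given. The repeat is done with the modification of "either shortening or lengthening the interval of reassessment based on their left" eye's result.
- Section D, on the prospects: "it is possible that we will not be able to capture this critical window in each participant, if one exists".

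**The concern.** To say that a given number of participants will yield at least 2 positives is a probability claim. It needs the frequency of the phenomenon and the probability to be reached. E.1 supplies neither, section C says there is no pertinent earlier work to supply them, and section D doubts that the window exists. A protocol that leaves existence open cannot also guarantee two sightings.

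The condition attached to the guarantee also differs from the procedure. E.1 assumes that both eyes of each participant are tested. Under section D, a participant whose left eye is positive is not called back.

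The sentence stands in the section on protection of human subjects, where it helps to justify giving drops to 15 volunteers who are not expected to benefit directly. A reader there should see that the chance of success depends on an unknown frequency.

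**Working it through.** **The plan's own figure.** The figure of 15 cannot be reproduced, because the protocol states no rate and no target probability. Every rate below is an assumption of this review.

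**Inputs from the protocol.** n = 15 participants (E.1); success is at least 2 positives (D and E.1), counted as participants in the closing paragraph of E.1; the right eye is tested only after a qualifying left-eye result (D).

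**Step 1. Is there a guarantee?** Let q be the share of participants positive in either eye, and let all 15 be tested. Then

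P(at least 2) = 1 − (1−q)^15 − 15·q·(1−q)^14.

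For any q below 1 the subtracted terms are greater than zero, so the probability is below 1.

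| Assumed q | (1−q)^15 | 15·q·(1−q)^14 | P(at least 2 of 15) |
|---|---|---|---|
| 5% | 0.4633 | 0.3658 | 17.1% |
| 10% | 0.2059 | 0.3432 | 45.1% |
| 20% | 0.0352 | 0.1319 | 83.3% |
| 30% | 0.0047 | 0.0305 | 96.5% |

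Solving for q at n = 15 gives 18.7% for an 80% chance and 27.9% for a 95% chance.

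**Step 2. Is 15 necessary?** The smallest n with at least an 80% chance of 2 positives is 59, 29, 14 and 9 at q = 5%, 10%, 20% and 30%. Fifteen is the smallest adequate number for 80% only if q lies between about 18.7% and 19.9%. At lower rates it is too few, and at higher rates fewer would do.

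**Step 3. Does the both-eyes premise matter numerically?** Assume a positive rate of 10% per eye at any interval, independent eyes, and a retest of every left-eye negative.

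- E.1 premise, 30 independent eyes counted as eyes: 1 − 0.9^30 − 30·0.1·0.9^29 = 1 − 0.0424 − 0.1413 = 81.6%.
- Section D scheme, counted by participant: q = 0.1 + 0.9·0.1 = 0.19, so 1 − 0.81^15 − 15·0.19·0.81^14 = 1 − 0.0424 − 0.1492 = 80.8%.

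The gap of 0.8 points equals 15·0.1²·0.81^14 = 0.0079. This is the chance that one participant alone supplies both instances, so the gap comes wholly from counting eyes instead of participants.

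**The case against.** The strongest defence is that the sentence should not be read literally. It is offered as the investigators' feeling, it carries a condition, the sentence after it is hedged, and section D openly says that the window may be missed. The main ground for 15 is that this is a proof of concept with no earlier data, and a pragmatic number is legitimate for such a study. The absence of a power calculation is then no fault in itself.

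Much of this stands. The number is acceptable, and the document as a whole does not hide the uncertainty. What does not stand is the sentence itself: neither the hedge nor the proof-of-concept label supplies the rate that a guarantee needs, and section D's caveat contradicts it.

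On the second eye, the defence is also partly right. In E.1, independently may simply mean separately, with each eye on its own day and at its own interval. A participant already positive in the left eye needs no second test to count. A reader might infer that conditional testing costs the study much of its chance of success, for instance if only some left-eye negatives were retested or if a participant's two eyes always agreed. The protocol does not support that. Any retest share would be an arbitrary choice, and section D changes the interval so that the second eye may succeed where the first did not. What remains is a mismatch of wording: both eyes in E.1, the right eye only under stated conditions in D.

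**Conclusion.** The point holds as a minor correction to the sample-size justification. E.1 claims an assurance that cannot follow from the protocol. With 15 participants the chance of at least 2 positives runs from about 17% to about 96% as the assumed participant-level rate goes from 5% to 30%. The protocol gives no ground for choosing within that range.

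The mismatch over the right eye is secondary and worth about 0.8 percentage points in the like-for-like case. That case assumes 10% per eye, independent eyes, the same rate at each interval, and every left-eye negative retested.

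Two stronger readings should be set aside. A reader might infer that 15 is too few; since the rate is unknown, the protocol does not show that, just as it does not show that 15 is enough. A reader might also call this an arithmetic error, but E.1 contains no calculation to get wrong. Nor is the complaint that the protocol omits something a statistical analysis plan could hold: it concerns a statement that the protocol makes.

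**What to change.** In section E.1:

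1. Delete the claim that 15 participants are necessary to guarantee two instances.
2. Replace the both-eyes premise with a description of right-eye testing as conditional, in line with section D.
3. Count participants positive in either eye, to match the participant-based criterion in the next paragraph of E.1.
4. State what can be said, for example: *The frequency is unknown. With 15 participants tested, the probability of at least 2 positive participants is about 17%, 45%, 83% and 96% if 5%, 10%, 20% and 30% of participants are positive in either eye (assumed rates); an 80% probability requires about 19%.*

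Optionally, add that 0 of 15 or 1 of 15 would remain compatible with frequencies up to 21.8% or 31.9% (upper limits of two-sided exact 95% intervals).

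The cost is a few sentences and a less favourable statement of the prospects. The number of participants, the procedures and the threshold of two stay as they are.

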There is a small risk of corneal abrasion with handheld applanation tonometry and gonioscopy, as in both cases direct contact is made with the cornea. This is extremely rare, and we are mitigating this risk by having a trained physician ([name]) perform these exams. These are both examination techniques used in the eye office daily.

The Reichert Tono-Pen Avia uses tips that contain natural rubber latex which may cause allergic reactions. Participants will be screened for a known allergy to natural rubber latex and will be asked to monitor for signs and symptoms of an allergic reaction following use of the Tono-Pen.

6. POTENTIAL BENEFITS:

This research study is not expected to directly benefit individual subjects but is likely to yield generalizable knowledge which contributes to the field. The information gained from this study may be useful and may help others who will be undergoing evaluations for anisocoria in the future.

7. CONFIDENTIALITY

Information obtained about participants during this research may be published, but they will not be identified. Information that is obtained concerning this research that can be identified will remain confidential to the extent possible within State and Federal law. The investigators associated with this study, the sponsor, and the Institutional Review Board will have access to identifying information. All records in South Carolina are subject to subpoena by a court of law. Study information will be securely stored in locked files and on password-protected network storage.

8. COMPENSATION:

We plan to provide participants with a gift card (Clincard) for their time spent conducting the study. We plan to request \$50 per participant. Potential medical student participants will be advised that their participation in the study will in no way affect their grades, evaluations or medical school standings.

9. WITHDRAWAL:

Participants may withdraw at any point, but the gift card will not be given as compensation unless participants complete the entire study. If participants fail to meet all inclusion criteria or meet any exclusion criteria during their initial visit and screening exam, they will not be able to proceed with the experiment and therefore will not receive compensation.

F. REFERENCES/LITERATURE CITATIONS

2. Eyster, E. F. "Oculomotor Palsy from Minor Head Trauma. An Initial Sign of Basal Intracranial Tumor." *JAMA: The Journal of the American Medical Association* 220, no. 8 (May 22, 1972): 1083–86.
<https://doi.org/10.1001/jama.220.8.1083>.
<https://doi.org/10.1038/sj.eye.6700625>
4. Karpecki, Paul M., Shane A. Foster, Stephen M. Montaquila, Shane R. Kannarr, Charles B. Slonim, Alan R. Meyer, Mina P. Sooch, et al. "Phentolamine Eye Drops Reverse Pharmacologically Induced Mydriasis in a Randomized Phase 2b Trial." *Optometry and Vision Science* 98, no. 3 (March 2021): 234–42.
<https://doi.org/10.1097/OPX.0000000000001656>.
